4.3.4 Dose Escalation, Stay or De-escalation Decision for Cohorts 2a, 3a and 4a

New cohorts for evaluation of dosing schedule with both V938 and pembrolizumab starting on C1D1 will be included via V938-001 Amendment 05 when the dose-finding decision has been made for Cohort 3, according to the rules described from the mTPI design (Section 4.3.3). When Cohort 3a, 4a, or 2a is open, 3 to 6 participants will be enrolled initially to each cohort, with potential to expand up to 14 participants. It is not necessary to have Cohort 3 or Cohort 4 expanding to 14 participants before transition to Cohort 3a, 4a, or 2a. The following algorithms are implemented for decision on dose-escalation, stay, or de-escalation for these new cohorts:

- Cohort 3:
 - If DLT evaluation indicates escalation, both Cohort 4 and Cohort 3a can be enrolled, with enrollment to Cohort 4 prioritized over Cohort 3a.
 - If DLT evaluation indicates stay, only Cohort 3a can be enrolled.
 - If DLT evaluation indicates de-escalation, only enroll Cohort 2a.

- Cohort 4:
 - If DLT evaluation indicates escalation or stay, Cohort 4a can be enrolled only if Cohort 3a also indicates dose escalation.
 - If DLT evaluation indicates de-escalation, wait for outcome from Cohort 3a.
- Cohort 3a:
 - If DLT evaluation indicates escalation, Cohort 4a can be enrolled only if Cohort 4 also indicates dose escalation.
 - If DLT evaluation indicates stay – expand cohort up to 14 participants.
 - If DLT evaluation indicates de-escalation, only enroll Cohort 2a.
- Cohort 4a:
 - If DLT evaluation indicates escalation or stay – cohort expand up to 14 participants
 - If DLT evaluation indicates de-escalation – expand Cohort 3a up to 14 participants
- Cohort 2a:
 - If DLT evaluation indicates escalation, may re-escalate to Cohort 3a.
 - If DLT evaluation indicates stay, cohort expand up to 14 participants.
 - If DLT evaluation indicates de-escalation, will end this dosing schedule.

The final selection of RP2D will be from Cohorts 2a, 3a, and 4a based on the totality of the available data.

4.4 Beginning and End of Study Definition

The overall study begins when the first participant (or their legally acceptable representative) provides documented informed consent. The overall study ends when the last participant completes the last study-related contact, withdraws consent, or is lost to follow-up (ie, the participant is unable to be contacted by the investigator).

Due to discontinuation of V938-001, all ongoing participants who have completed C7D1 V938 plus pembrolizumab treatment may be enrolled to an extension study to continue pembrolizumab monotherapy for total of 35 cycles since first dose in V938-001 and to be monitored per the extension study as appropriate.

4.4.1 Clinical Criteria for Early Study Termination

Recruitment in the study or at (a) particular study site(s) may be stopped due to insufficient compliance with the protocol, GCP and/or other applicable regulatory requirements, procedure-related problems, or the number of discontinuations for administrative reasons is too high.

Study recruitment/treatment will be paused if one of the following occurs:

- Any death (not due to disease progression) that is possibly, probably, or definitely related to V938 or V938 in combination with pembrolizumab.
- Two Grade 4 AEs that are possibly, probably, or definitely related to V938 or V938 in combination with pembrolizumab.

Early study termination will be the result of the criteria specified below:

- Incidence or severity of adverse drug reactions in this or other studies suggest a potential health hazard to participants
- Plans to modify or discontinue the development of the study medication
- Quality or quantity of data recording is inaccurate or incomplete

Ample notification will be provided in the event of Sponsor decision to no longer supply V938 or pembrolizumab.

5 STUDY POPULATION

Male/female participants at least 18 years of age with advanced/metastatic solid tumors who have progressed on, been ineligible for, or refused other active therapies including targeted therapy based on mutation status (eg, MSI-H, BRAF) per standard of care, will be enrolled in this study.

Prospective approval of protocol deviations to recruitment and enrollment criteria, also known as protocol waivers or exemptions, is not permitted.

5.1 Inclusion Criteria

To be eligible for inclusion in this study, the participant must:

Type of Participant and Disease Characteristics

1. **For Dose-escalation Cohorts:** Have a histologically confirmed advanced/metastatic solid tumor and have received, been intolerant to, or been ineligible for treatments known to confer clinical benefit. Solid tumors of any type are eligible for enrollment. Tumor types of greatest interest include, but are not limited to, malignant melanoma, HNSCC, and breast carcinoma.

For Arm A of Cohort Expansion: Have a histologically confirmed Stage III (unresectable) or Stage IV cutaneous melanoma and have received and progressed following 1 or 2 prior lines of systemic treatments for metastatic melanoma which must include 1 line of treatment with PD-1 or PD-L1 immune checkpoint inhibitor either as monotherapy or in combination with other therapy.

For Arm B of Cohort Expansion: Have a histologically confirmed advanced HNSCC and have received and progressed following 1 or 2 prior lines of systemic treatments for metastatic HNSCC which must include 1 line of treatment with PD-1 or PD-L1 immune checkpoint inhibitor either as monotherapy or in combination with other therapy.

For Arms A and B of Cohort Expansion: PD-1 treatment progression is defined by meeting all of the following criteria:

- a. Has received at least 2 doses of an approved anti-PD-1/L1 mAb.
 - b. Has shown disease progression after anti-PD-1/L1 as defined by RECIST v1.1. The initial evidence of disease progression is to be confirmed by a second assessment no less than 4 weeks from the date of the first documented disease progression, in the absence of rapid clinical progression (as defined in 1.c).
 - c. Progressive disease has been documented within 12 weeks from the last dose of anti-PD-1/L1 mAb.
 - i. Progressive disease is determined according to iRECIST.
 - ii. This determination is made by the investigator. Once disease progression is confirmed, the initial date of disease progression documentation will be considered the date of disease progression.
2. Have a performance status of 0 or 1 on the ECOG Performance Scale.
 3. Show adequate organ function as defined in [Table 2](#). These samples must be collected within 72 hours prior to C1D1.

Table 2 Adequate Organ Function Laboratory Values

System	Laboratory Value
Hematological	
Absolute neutrophil count	$\geq 1,500/\text{mcL}$
Platelets	$\geq 100,000/\text{mcL}$
Hemoglobin	$\geq 9 \text{ g/dL}$ or $>5.6 \text{ mmol/L}^a$
Renal	
Serum creatinine or CrCl (measured or calculated) ^b or GFR in place of CrCl	$\leq 1.5 \times \text{ULN}$ or $>30 \text{ mL/min}$ for participants with creatinine levels $>1.5 \times \text{ULN}$
Hepatic	
Total bilirubin (serum)	$\leq 1.5 \times \text{ULN}$ or Direct bilirubin $<\text{ULN}$ for participants with total bilirubin levels $>1.5 \times \text{ULN}$
AST (SGOT) and ALT (SGPT)	$\leq 2.5 \times \text{ULN}$ or $\leq 5 \times \text{ULN}$ for participants with liver metastases
Coagulation	
INR or PT	$<1.5 \times \text{ULN}$ (unless participant is receiving anticoagulant therapy, in which case PT/INR or aPTT should be within the therapeutic range of intended use of anticoagulants)
aPTT	

Abbreviations: ALT (SGPT) = alanine aminotransferase (serum glutamic pyruvic transaminase); aPTT = activated partial thromboplastin time; AST (SGOT) = aspartate aminotransferase (serum glutamic oxaloacetic transaminase); CrCl = creatinine clearance; GFR = glomerular filtration rate; INR = international normalized ratio; PT = prothrombin time; ULN = upper limit of normal.
 
^a Criteria must be met without packed red blood cell (PRBC) and platelet transfusion within the prior 2 weeks. Participants can be on stable dose of erythropoietin (\geq approximately 3 months).
 
^b Creatinine clearance (CrCl) should be calculated per institutional standard.
 
Note: This table includes eligibility-defining laboratory value requirements for treatment; laboratory value requirements should be adapted according to local regulations and guidelines for the administration of specific chemotherapies.
	

Demographics

- Are male or female, and must be at least 18 years of age at the time of signing the informed consent.

Male Participants

Contraceptive use by men should be consistent with local regulations regarding the methods of contraception for those participating in clinical studies.

- Male participants are eligible to participate if they agree to the following during the intervention period and for at least 120 days:

- Be abstinent from heterosexual intercourse as their preferred and usual lifestyle (abstinent on a long-term and persistent basis) and agree to remain abstinent

OR

- Must agree to use contraception unless confirmed to be azoospermic (vasectomized or secondary to medical cause (Appendix 5) as detailed below:
 - Agree to use a male condom plus partner use of an additional contraceptive method when having penile-vaginal intercourse with a WOCBP who is not currently pregnant. Note: Men with a pregnant or breastfeeding partner must agree to remain abstinent from penile-vaginal intercourse or use a male condom during each episode of penile-vaginal penetration.
 - Contraceptive use by men should be consistent with local regulations regarding the methods of contraception for those participating in clinical studies.

Female Participants

Contraceptive use by women should be consistent with local regulations regarding the methods of contraception for those participating in clinical studies.

6. A female participant is eligible to participate if she is not pregnant or breastfeeding, and at least one of the following conditions applies:

- Is not a woman of childbearing potential (WOCBP)

OR

- Is a WOCBP and using a contraceptive method that is highly effective (with a failure rate of <1% per year), or be abstinent from heterosexual intercourse as their preferred and usual lifestyle (abstinent on a long term and persistent basis), as described in Appendix 5 during the intervention period and for at least 120 days after the last dose of study intervention. The investigator should evaluate the potential for contraceptive method failure (ie, noncompliance, recently initiated) in relationship to the first dose of study intervention.
- A WOCBP must have a negative highly sensitive pregnancy test (urine or serum as required by local regulations) within 72 hours before C1D1.
- If a urine test cannot be confirmed as negative (eg, an ambiguous result), a serum pregnancy test is required. In such cases, the participant must be excluded from participation if the serum pregnancy result is positive.

Additional requirements for pregnancy testing during and after study intervention are located in Appendix 2.

The investigator is responsible for review of medical history, menstrual history, and recent sexual activity to decrease the risk for inclusion of a woman with an early undetected pregnancy.

Informed Consent

7. The participant (or legally acceptable representative) has provided documented informed consent/assent for the study. The participant may also provide consent for future biomedical research. However, the participant may participate in the main study without participating in future biomedical research. See country-specific information in Appendix 7.

Additional Categories

8. Has well controlled HIV (for HIV-infected participants) on ART, defined as:
 - a. Participants on ART must have a CD4+ T-cell count >350 cells/mm³ at time of screening.
 - b. Participants on ART must have achieved and maintained virologic suppression defined as confirmed HIV RNA level below 50 or the LLOQ (below the limit of detection) using the locally available assay at the time of screening and for at least 12 weeks prior to screening.
 - c. Participants on ART must have been on a stable regimen, without changes in drugs or dose modification, for at least 4 weeks prior to study entry (Day 1).
 - d. The combination ART regimen must not contain any antiretroviral medications other than: abacavir, dolutegravir, emtricitabine, lamivudine, raltegravir, rilpivirine, or tenofovir.
9. **Have lesions as defined below:**
 - a. For All Participants: Have at least 1 cutaneous or subcutaneous lesion amenable to IT injection and must be measurable and meet 1 of the following criteria (per RECIST 1.1):
 - i. A cutaneous or subcutaneous lesion ≥ 1 cm in longest diameter for solid tumors, or ≥ 1.5 cm in short axis for a nodal lesion in participants with solid tumor. The longest diameter for an injectable lesion must be ≤ 10 cm for both solid tumors and nodal lesions in participants with solid tumors.
 - ii. Multiple coalescing, superficial lesions that in aggregate have a longest diameter of ≥ 1 cm and ≤ 10 cm.
 - b. For Expansion Cohorts (Arms A and B) ONLY: Have at least 1 distant and/or discrete noninjected lesion that is measurable per RECIST 1.1 criteria.

10. For Dose-escalation Cohorts 2a, 3a, or 4a and Expansion Cohorts (Arms A and B)
ONLY: Have baseline biopsy performed from one of the injectable lesions that are planned for IT injection and with tumor tissue provided.

5.2 Exclusion Criteria

The participant must be excluded from the study if the participant:

Medical Conditions

1. Has had chemotherapy, definitive radiation, or biological cancer therapy within 4 weeks (2 weeks for palliative radiation) prior to the first dose of study intervention or has not recovered to CTCAE Grade 1 or better from any AEs that were due to cancer therapeutics administered more than 4 weeks earlier (this includes participants with previous immunomodulatory therapy with residual immune-related AEs). Participants receiving ongoing replacement hormone therapy for endocrine immune-related AEs will not be excluded from participation in this study.
2. Has a history of a second malignancy, unless potentially curative treatment has been completed with no evidence of malignancy for 2 years.

Note: The time requirement does not apply to participants who underwent successful definitive resection of basal cell carcinoma of the skin, superficial bladder cancer or in situ cervical cancer, or other in-situ cancers.

3. Has clinically active central nervous system metastases and/or carcinomatous meningitis. Participants with previously treated brain or meningeal metastases may participate and be eligible for treatment provided they are stable and asymptomatic (without evidence of progression by MRI scan of the brain separated by at least 4 weeks after treatment), have no evidence of new or enlarging brain metastases, are evaluated within 4 weeks prior to first study intervention administration, and are off immunosuppressive doses of systemic steroids at least 2 weeks prior to enrollment.

Note: Participants with asymptomatic, previously untreated brain metastases may participate provided there are ≤ 3 total lesions in the brain and the longest diameter of each lesion is < 1 cm. Stability of these lesions does not need to be confirmed by repeat imaging. Participants may not receive steroids to treat these lesions.

4. Has had a severe hypersensitivity reaction to treatment with the monoclonal antibody/components of the study intervention or has a history of any contraindication or has a severe hypersensitivity to any components of pembrolizumab (\geq Grade 3).
5. Has an active infection requiring therapy.
6. Has a history of (noninfectious) pneumonitis that required steroids or current pneumonitis.

7. Has an active autoimmune disease that has required systemic treatment in the past 2 years (ie, with use of disease-modifying agents, corticosteroids, or immunosuppressive drugs) except vitiligo or resolved childhood asthma/atopy. Replacement therapy, such as thyroxine, insulin, or physiologic corticosteroid replacement therapy for adrenal or pituitary insufficiency, is not considered a form of systemic treatment and is allowed.
8. Is on chronic systemic steroid therapy in excess of replacement doses (prednisone \leq 10 mg/day is acceptable), or on any other form of immunosuppressive medication. Use of nonsystemic steroids is permitted.
9. Participants with known Hepatitis B or C infections or known to be positive for hepatitis B antigen/hepatitis B virus DNA or hepatitis C antibody or RNA. Active hepatitis C is defined by a known positive Hepatitis C antibody result and known quantitative hepatitis C virus RNA results greater than the lower limits of detection of the assay.
10. HIV-infected participants with a history of Kaposi's sarcoma and/or Multicentric Castleman's Disease.
11. Has a known psychiatric or substance abuse disorder that would interfere with the participant's ability to cooperate with the requirements of the study.
12. Is pregnant or breastfeeding or expecting to conceive or father children within the projected duration of the study, starting with the Screening Visit through 120 days after the last dose of study intervention.
13. Has not fully recovered from any effects of major surgery without significant detectable infection. Surgical procedures that required general anesthesia must be completed at least 2 weeks before first study intervention administration. Surgery requiring regional/epidural anesthesia must be completed at least 72 hours before first study intervention administration and participants should be recovered.

Prior/Concomitant Therapy

14. Has received a live-virus vaccine within 30 days of planned treatment start. Seasonal flu vaccines that do not contain live virus are permitted.
15. Has received prior treatment with either NDV or hIL-12.

Prior/Concurrent Clinical Study Experience

16. Is currently participating and receiving study intervention in a study of an investigational agent or has participated and received study intervention in a study of an investigational agent or has used an investigational device within 28 days of administration of V938.

Note: Participants who have entered the follow-up phase of an investigational study may participate as long as it has been 4 weeks since the last dose of the previous investigational agent.

Note: Prior exposure to immunotherapeutics is allowed, including PD-1 and PD-L1 inhibitors, provided participant did not experience a \geq Grade 3 drug-related toxicity on monotherapy with a PD-1 or PD-L1 inhibitor.

Diagnostic Assessments

Other Exclusions

17. Has an active egg allergy.
18. Has a history of re-irradiation for HNSCC at the projected injection site.
19. Has a tumor(s) in direct contact or encases a major blood vessel and has ulceration and/or fungation onto the skin surface at the projected injection site.
20. Works on a farm or other profession if bird exposure is prominent.
21. For Expansion Cohorts ONLY: Has uveal or ocular melanoma.
22. For Expansion Cohorts ONLY: Has mucosal melanoma.

5.3 Lifestyle Considerations

5.3.1 Meals and Dietary Restrictions

Participants should maintain a normal diet unless modifications are required to manage AEs such as diarrhea, nausea, or vomiting.

5.3.2 Caffeine, Alcohol, and Tobacco Restrictions

None.

5.3.3 Activity Restrictions

None.

5.4 Screen Failures

Screen failures are defined as participants who consent to participate in the clinical study, but are not subsequently entered in the study. A minimal set of screen failure information is required to ensure transparent reporting of screen failure participants to meet the Consolidated Standards of Reporting Trials (CONSORT) publishing requirements and to respond to queries from regulatory authorities. Minimal information includes demography, screen failure details, eligibility criteria, and any AEs or SAEs meeting reporting requirements as outlined in the data entry guidelines.

5.5 Participant Replacement Strategy in Dose Escalation

In order to adequately evaluate the safety of the doses administered in this study, all participants enrolled must meet the criteria for evaluability for Cycle 1 and Cycle 2 for Cohorts 1-4 of dose escalation and must meet the criteria for evaluability for Cycle 1 for Cohorts 2a-4a. Participants are considered nonevaluable and will be replaced if:

They are allocated but not treated.

They discontinue from the study prior to completing all the safety evaluations for reasons other than treatment-related AEs.

They receive less than 75% of the total V938 PFU injection or pembrolizumab infusion in the DLT evaluation period (eg, if the infusion had to be discontinued due to an infusion reaction) and did not experience a DLT.

Participants who are not evaluable will be replaced unless accrual to the cohort has stopped. Nonevaluable participants will not be counted toward the total number of participants in the cohort for DLT evaluation.

If a participant experiences a DLT in the DLT evaluation period, study intervention may be discontinued following discussion between the Sponsor and investigator. However, if the participant is deriving clinical benefit from the study intervention, the participant may be allowed to continue after discussion between the Sponsor and the investigator.

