Participants should receive appropriate supportive care measures as deemed necessary by the treating investigator. Suggested supportive care measures for the management of AEs with potential immunologic etiology are outlined along with the dose modification guidelines in [Table 8](#). Where appropriate, these guidelines include the use of oral or IV treatment with corticosteroids, as well as additional anti-inflammatory agents if symptoms do not improve with administration of corticosteroids. Note that several courses of steroid tapering may be necessary as symptoms may worsen when the steroid dose is decreased. For each disorder, attempts should be made to rule out other causes such as metastatic disease or bacterial or viral infection, which might require additional supportive care. The treatment guidelines are intended to be applied when the investigator determines the events to be related to pembrolizumab.

Note: If after the evaluation of the event, it is determined not to be related to pembrolizumab, the investigator does not need to follow the treatment guidance. Refer to [Table 8](#) for guidelines regarding dose modification and supportive care.

It may be necessary to perform conditional procedures such as bronchoscopy, endoscopy, or skin photography as part of evaluation of the event.

6.6 **Dose Modification (Escalation/Titration/Other)**

6.6.1 **Dose Administration/Escalation**

Details on preparation and administration of V938 and pembrolizumab are provided in the appropriate Pharmacy/Laboratory Procedures Manual.

6.6.2 **Definition of Dose-limiting Toxicity**

All toxicities will be graded using CTCAE Version 4.0, with exception of CRS, based on the investigator assessment. The CRS grading system used in this protocol is adapted from the ASTCT Consensus Grading for CRS [Lee, D. W., et al 2019].

The DLT observation period for Cohorts 1-4 will be 42 days during Cycles 1 and 2 (ie, the first monotherapy run-in cycle [Cycle 1] and the first combination therapy cycle [Cycle 2]). The DLT observation period for Cohorts 2a-4a will be 21 days during Cycle 1 only.

The occurrence of any of the following toxicities during the DLT observation period will be considered a DLT, if assessed by the investigator to be possibly, probably, or definitely related to study intervention administration:

1. Grade 4 nonhematologic toxicity (not laboratory)
2. Grade 4 hematologic toxicity lasting ≥ 7 days, except thrombocytopenia:

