 - a. Grade 4 thrombocytopenia of any duration
 - b. Grade 3 thrombocytopenia associated with clinically significant bleeding
3. Grade 3 nonhematologic AE with the following exceptions:
 - a. Grade 3 fatigue lasting ≤ 72 hours
 - b. Grade 3 diarrhea, nausea, or vomiting lasting ≤ 72 hours without use of antiemetics or antidiarrheals per standard of care
 - c. Grade 3 rash without use of corticosteroids or anti-inflammatory agents per standard of care.
4. Any Grade 3 or Grade 4 nonhematologic laboratory value if:
 - a. Clinically significant medical intervention is required to treat the participant, or
 - b. The abnormality leads to hospitalization, or
 - c. The abnormality persists for >1 week
 - d. The abnormality results in a DILI (see Sections 8.4.1 and 8.4.7 for criteria)

Exceptions: Clinically nonsignificant, treatable, or reversible laboratory abnormalities including liver function tests, uric acid, etc.
5. Febrile neutropenia Grade 3 or Grade 4:
 - a. Grade 3 is defined as ANC $<1000/\text{mm}^3$ with a single temperature of $>38.3^\circ\text{C}$ (101°F) or a sustained temperature of $\geq 38^\circ\text{C}$ (100.4°F) for more than 1 hour.
 - b. Grade 4 is defined as ANC $<1000/\text{mm}^3$ with a single temperature of $>38.3^\circ\text{C}$ (101°F) or a sustained temperature of $\geq 38^\circ\text{C}$ (100.4°F) for more than 1 hour, with life-threatening consequences and urgent intervention indicated.
6. Prolonged delay (>2 weeks) in initiating Cycle 3 (for Cohorts 1-4) or Cycle 2 (for Cohorts 2a-4a) due to study intervention-related toxicity.

7. Any study intervention-related toxicity that causes the participant to discontinue intervention during the DLT evaluation period.
8. Missing >1 injection of V938 as a result of drug-related AE(s) during the first 2 cycles (for Cohorts 1-4) or during the first cycle (for Cohort 2a-4a).
9. Grade 5 toxicity.

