Grade 1	None	Increase monitoring of vital signs and oxygen saturation, as medically indicated, until the participant is deemed medically stable, in the opinion of the investigator.	Recommended. Participant may be premedicated with antipyretic, eg, acetaminophen 500 to 1000 mg po 1.5 h (\pm 30 min), or with an antihistamine, prior to study intervention administration, or at the discretion of the investigator.
Grade 2	Delay next dose until AE is resolved, retreatment at the same dose level. For recurrent Grade 2, retreatment may be allowed at the same dose level or 1 dose level down upon discussion with the Sponsor	Increase monitoring of vital signs and oxygen saturation, as medically indicated, until the participant is deemed medically stable, in the opinion of the investigator. Additional appropriate medical therapy may include, but is not limited to: 
 • IV fluids • NSAIDs • Acetaminophen • Narcotics • Oxygen Perform fever workup to exclude infectious etiologies; treat neutropenia if present.	

CRS Grade per ASTCT ^a	V938 Dose Modification	CRS Management	Premarket for Subsequent Doses
Grade 3 or Grade 4	Permanently discontinue V938	
Additional appropriate medical therapy may include, but is not limited to:
 
 • IV fluids • NSAIDS • Acetaminophen • Narcotics • Oxygen • Vasopressors • Corticosteroids • Anti-IL6 (eg, tocilizumab) • Empiric antibiotics 
Participants with \geq Grade 3 CRS need to be monitored very closely, likely in an intensive care setting.
	NA

Abbreviations: ASTCT= American Society for Transplantation and Cellular Therapy ; CRS=cytokine release syndrome; IL=interleukin; IV=intravenous; NSAIDS=nonsteroidal anti-inflammatory drugs; PO=by mouth.

^a CRS Grading adapted from ASTCT Consensus Grading (see [Table 6](#)).

If toxicity does not resolve to Grade 0 or 1 within 6 weeks after last intervention, V938 should be discontinued. With investigator and Sponsor agreement, participants with a laboratory AE still at Grade 2 after 6 weeks may continue intervention in the study only if asymptomatic and controlled.

After any Grade 4, drug-related AE, participants should not restart study intervention without consultation with the Sponsor. (Toxicity must have resolved to Grade 0 or 1 or baseline prior to restarting.)

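### Section 5.5's early-exit replacement bullet has no exception for a DLT already observed, so read literally it drops that DLT from the Table 1 count

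*Combined protocol and SAP*

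**What the plan says.** Section 5.5 lists three routes by which a dose-escalation participant becomes nonevaluable and is replaced.

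- The first is allocation without treatment.
- The second is early exit: "They discontinue from the study prior to completing all the safety evaluations for reasons other than treatment-related AEs".
- The third is dose shortfall: "They receive less than 75% of the total V938 PFU injection or pembrolizumab infusion in the DLT evaluation period". It is qualified at its end: "eg, if the infusion had to be discontinued due to an infusion reaction) and did not experience a DLT".

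The consequence is the same for all three: "Nonevaluable participants will not be counted toward the total number of participants in the cohort for DLT evaluation". Replacement follows unless accrual to the cohort has stopped.

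Section 6.6.2 defines the endpoint by occurrence alone: "The occurrence of any of the following toxicities during the DLT observation period will be considered a DLT", provided the investigator judges the event related. It does not require the participant to complete the window, which is 42 days for Cohorts 1-4 and 21 days for Cohorts 2a-4a.

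Section 9.5.1 defines the DLT-evaluable population by sending the reader to Section 6.6.2 for the evaluability criteria. Section 6.6.2 contains none; they are in Section 5.5.

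**The concern.** Two adjacent bullets deal with participants whose DLT assessment is incomplete. One protects a DLT that has already been seen; the other does not. For early exit, the only test is the reason for leaving. A participant who has a DLT on Day 5 and withdraws consent on Day 15 meets that test, and nothing elsewhere in the documents says that a participant with a DLT is always evaluable.

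Table 1 takes two inputs: the number of participants with a DLT and the number evaluable. Following Section 5.5 as written removes such a participant from both. The same exclusion carries into the DLT-evaluable population, and so into the pool-adjacent-violators estimates and the 80% credible interval at the RP2D (Section 9.6.2). DLT is a primary endpoint, and this is a first-in-human study, so the rule that decides whether a DLT counts should have only one reading.

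**Working it through.** **1. Reproduce Table 1.** Inputs from Section 4.3.3: target rate 30%, Beta(1,1) prior, ε1 = ε2 = 0.03. With x DLTs in n participants the posterior is Beta(1+x, 1+n−x). Each interval's posterior probability is divided by its length, and the largest value gives the decision: (0, 0.27) escalate, (0.27, 0.33) stay, (0.33, 1) de-escalate. A dose is marked DU if P(rate > 0.30) exceeds 0.95. The documents do not state the 0.95 cutoff; it is an assumption. With it, all 78 legible cells in rows 0 to 6 match.

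Example, 1/3, Beta(2,3): F(t) = 1 − (1−t)^4 − 4t(1−t)^3, so F(0.27) = 0.296 and F(0.33) = 0.401.
- Escalate: 0.296/0.27 = 1.10
- Stay: (0.401 − 0.296)/0.06 = 1.76
- De-escalate: (1 − 0.401)/0.67 = 0.89

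Stay is largest, as printed.

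Example, 0/3, Beta(1,4): F(t) = 1 − (1−t)^4. The three values are 2.65, 1.37 and 0.30, so escalate, as printed.

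**2. Remove one DLT.** If a participant with a DLT is discarded and the replacement has none, x falls by 1 and n is unchanged.

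| All DLTs counted | Section 5.5 read literally |
|---|---|
| 1/3 S | 0/3 E |
| 2/3 D | 1/3 S |
| 2/6 S | 1/6 E |
| 4/6 DU | 3/6 S |
| 3/14 S | 2/14 E |

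In the last row the crude rate falls from 3/14 = 21.4% to 2/14 = 14.3%. The shift needs a DLT-free replacement; at a true rate of 30% that has probability 0.70.

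**3. Long-run effect.** Let p be the true DLT rate, and let w1 and w0 be the proportions leaving for other reasons with and without a DLT. The rate among evaluable participants is

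p(1−w1) / [p(1−w1) + (1−p)(1−w0)].

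The documents give no exit rates, so w1 and w0 are assumptions. From Table 1, P(escalate) is P(X = 0) at n = 3 and P(X ≤ 1) at n = 6.

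| p | w1 | w0 | Rate counted | P(escalate), n=3 | P(escalate), n=6 |
|---|---|---|---|---|---|
| 0.30 | 0 | 0 | 0.300 | 0.343 | 0.420 |
| 0.30 | 0.10 | 0 | 0.278 | 0.376 | 0.468 |
| 0.30 | 0.20 | 0 | 0.255 | 0.413 | 0.521 |
| 0.30 | 0.30 | 0 | 0.231 | 0.455 | 0.580 |
| 0.40 | 0 | 0 | 0.400 | 0.216 | 0.233 |
| 0.40 | 0.10 | 0 | 0.375 | 0.244 | 0.274 |
| 0.40 | 0.20 | 0 | 0.348 | 0.277 | 0.323 |
| 0.40 | 0.30 | 0 | 0.318 | 0.317 | 0.382 |
| 0.30 | 0.10 | 0.10 | 0.300 | 0.343 | 0.420 |

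The last row is the benign case: when w1 = w0 the factors cancel and the expected rate is p.

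**The case against.** The best defence is that the gap is narrow and looks like a drafting omission. The second bullet needs exit from the study. Section 7.1 says that stopping treatment is not withdrawal, and it keeps a participant who progresses under monitoring. Scheduled imaging starts at week 9, after both DLT windows. What remains is mainly consent withdrawal, or death from disease, after a DLT and within 21 or 42 days. The third bullet's exception suggests that the authors meant a DLT always to count, and Section 6.6.2 points the same way. All of this stands as a limit on frequency. It does not settle the conflict, because Section 5.5 is the operative rule for who is counted and Section 9.5.1 refers to the wrong section.

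A reader might go further and infer that toxicity is removed from the dose decision. The documents do not support that. Section 4.2 has all safety data reviewed before each escalation, Section 4.1.1 bases the RP2D on the totality of the data, Section 4.4.1 pauses the study for a related death or two related Grade 4 events whether or not the participant is evaluable, and Section 9.5.1 analyses safety in all treated participants. None of these, however, puts the lost DLT back into Table 1 or the DLT-rate estimate.

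A reader might also infer that the dose-shortfall bullet favours escalation, because its own example is an infusion reaction. It replaces only participants without a DLT. Each would have contributed a non-DLT, and the replacement may contribute a DLT, so replacement cannot lower the DLT count. Section 6.6.2 already makes DLTs of "Any study intervention-related toxicity that causes the participant to discontinue intervention during the DLT evaluation period" and of missing more than one V938 injection for drug-related events. In Cohorts 2a-4a, missing one of four leaves exactly 75%, which is not below the limit. Scoring lesser shortfalls as DLTs would change the DLT definition, not repair a contradiction.

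**Conclusion.** The point holds for the early-exit bullet only. As written, Section 5.5 can exclude a DLT that Section 6.6.2 says has occurred, and no other section restores it. When that happens, one lost DLT can move Table 1 a step or more towards a higher dose: stay to escalate at 1/3 or 2/6, or DU to stay at 4/6. This assumes that the replacement has no DLT.

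The average effect is unknown. It is zero in expectation if exits are unrelated to having had a DLT. If only participants with a DLT leave, at 10% to 30%, P(escalate) at n = 6 rises from 0.233 to between 0.274 and 0.382 at a true rate of 40%. Those exit rates are assumptions, and the figures are a sensitivity range, not a forecast.

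Closure of the study does not dispose of the point, because the DLT rates and the credible interval at the RP2D still have to be reported.

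**What to change.** 1. In Section 5.5, give the second bullet the same exception as the third, so that it applies only to participants without a DLT.
2. State in Sections 5.5 and 9.5.1 that any participant with a DLT in the evaluation window is DLT-evaluable, whatever the later reason for leaving.
3. In Section 9.5.1, change the cross-reference for evaluability from Section 6.6.2 to Section 5.5.

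If the protocol will not be amended again, Section 9.1 allows the clarification to go into the sSAP before analysis.

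The change needs no new data or participants, and leaves the DLT definition and dose-modification tables alone. Its cost is a possibly slightly higher DLT count and slightly slower escalation. Counting every DLT while still replacing DLT-free leavers gives a rate of p/[p + (1−p)(1−w0)]. At p = 0.30 and w0 = 0.10 that is 0.30/(0.30 + 0.63) = 0.323, and P(escalate) at n = 6 is 0.373 instead of 0.420. For dose finding in a first-in-human study, an error in that direction is the easier one to accept.
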